## 1 Introduction

### 1.1 Scope of document

The SAP documents contain detailed information to aid the production of Statistics & Programming input into the Clinical Study Report (CSR) for trial “**CLHW090X2102**”.

The Statistical analysis plan (SAP) describes the implementation of the statistical analysis planned in the protocol.

### 1.2 Study reference documentation

Protocol Version v04 is referred for the current SAP.

### 1.3 Study objectives

#### Primary objective(s)

Primary objective(s)	Endpoints related to primary objective(s)

 
• Part 1: To assess the safety and tolerability of doses of LHW090 in patients with moderate renal impairment to inform design of Part 2.
 
• Part 2: To assess the renal safety of LHW090 in patients with moderate renal impairment.
 
	
 
• Part 1: Safety endpoints (including adverse events and serious adverse events) up to and including the EOS; plasma pharmacokinetic parameters, and serum creatinine
 
• Part 2: Proportion of patients who develop a renal event as defined by a <math>\geq 0.3</math> mg/dL increase in serum creatinine from baseline
 

[figure not shown]
#### Secondary objective(s)

Secondary objective(s)	Endpoints related to secondary objective(s)

 
• All Parts: To evaluate the pharmacokinetics of LHW090 and its active metabolite, LHV527, in patients with moderate renal impairment.
 
	
 
• Plasma pharmacokinetic parameters (Cmax, Tmax, AUC)
 

 
• All Parts: To assess the safety and tolerability of LHW090 relative to placebo in patients with moderate renal impairment.
 
	
 
• Safety endpoints (including adverse events and serious adverse events) up to and including the EOS
 

#### **1.4 Study design and treatment**

The study purpose is to determine whether LHW090 displays the clinical safety profile to support further development in patients with moderately impaired renal function.

This is a randomized, double-blind, parallel group, placebo-controlled study, in two sequential parts to evaluate the renal safety, tolerability and pharmacokinetics of LHW090 in patients with moderately impaired renal function. Patients aged 40 to 85 (inclusive) with an estimated glomerular filtration rate (eGFR) between 30 and 59 mL/min/1.73m^2 at screening (inclusive) on a stable dose of an angiotensin receptor blocker (ARB) will be considered for this study.

**Part 1 will be enrolled as a cohort of 12 subjects (2:1 LHW090 and placebo). Patients will be domiciled from Day -2 to Day 14.**

Corporate Confidential Information

**Part 2 First 16 patients will be domiciled for 1 week, from day -2 to Day 7. Rest of the dosing will be done off site, and placebo.**

**Part 2 will enroll n=72 patients randomized 3:3:2 to LHW090**

Corporate Confidential Information

The study will be conducted in two parts. Part 1 will enroll a single cohort of 12 patients who will be randomized in a 2:1 ratio of LHW090 to placebo. An intra-patient dose escalation scheme will be employed starting at a [redacted] once daily dose for the first four day cycle, and then the dose will be escalated [redacted] once daily for the next four days and then [redacted] once daily for four days. If a renal event occurs during the treatment periods of the study or any of the individual stopping criteria are met, then dosing will be stopped for that individual patient. For the purposes of this study, a renal event will be defined as a reproducible increase from baseline serum creatinine of  $\geq 0.3$  mg/dL confirmed on a repeat measurement within 24-48 hours ([Mehta et al 2007](#), [Khwaja 2012](#)). Throughout the study, any serum creatinine assessment that is increased  $\geq 0.3$  mg/dL compared to baseline will trigger a repeat assessment of serum creatinine after 24 hours to confirm whether criterion for a renal event is met.

Corporate Confidential Information

Part 2 will be double-blind and placebo-controlled to assess the safety and tolerability of 2 dose levels of LHW090, [redacted] once daily for 4 weeks. Approximately 72 patients will be enrolled in Part 2 and randomized in a 3:3:2 ratio to LHW090

[redacted] and placebo. Therefore, in Part 2, approximately 27 patients are expected to be randomized to each of the active doses, and 18 patients are expected to be randomized to placebo. Randomization will be stratified by ARB dose (see Protocol) at the time of enrollment. Patients who meet the eligibility criteria at screening will have baseline assessments of renal function [redacted] collected on Day -1 prior to beginning the treatment phase on Day 1. Centrally-analyzed laboratory assessments performed at screening will be used to determine patient eligibility for the trial.

Corporate Confidential Information

The first 16 patients in Part 2 will be domiciled for the first 7 days of dosing to ensure careful monitoring of renal function and pharmacokinetic parameters. On Day 7 at the investigator's discretion, the patients will be released to complete the remaining 3 weeks of the treatment phase.

Corporate Confidential Information

## **2 First interpretable results (FIR)**

FIR contains the key outputs

Corporate Confidential Information

## **4 Statistical methods: Analysis sets**

For subjects for which the actual treatment received does not match the randomized treatment the treatment actually received will be used for the analysis.

All subjects that received study drug and with no protocol deviations with relevant impact on safety will be included in the safety analysis set.

The PK analysis set will include all subjects with at least one available valid (i.e. not flagged for exclusion) PK concentration measurement, who received any study drug and experienced no protocol deviations with relevant impact on PK data.

Corporate Confidential Information

The analysis sets and protocol deviation codes are related as follows:

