11.1 Analysis sets

For all analysis sets, subjects will be analyzed according to the study treatment(s) received.

The safety analysis set will include all subjects that received any study drug.

The PK analysis set will include all subjects with available PK data and no protocol deviations with relevant impact on PK data.

The PD analysis set will include all subjects with available PD data and no protocol deviations with relevant impact on PD data.

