**Table 4-1 Protocol deviation codes and analysis sets**

Category Deviation code	Text description of deviation	Data exclusion
Subjects are excluded from all (safety, PK, PD) analysis in case of these PDs:		
INC01	Written informed consent was not obtained prior to performing study assessment.	Excluded from safety, PK, PD analysis set
TRT03	Subject did not receive any dose of study treatment.	Excluded from Safety, PK and PD analysis set

If updates to this table are needed, an amendment to the SAP needs to be implemented prior to DBL.

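### SAP 4 and Table 4-1 can remove dosed subjects from the safety analysis set, although protocol 11.1 keeps everyone who took any study drug

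*SAP*

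**What the plan says.** Protocol 11.1 defines the safety set in one sentence: "The safety analysis set will include all subjects that received any study drug". Its next definition does use deviations: "The PK analysis set will include all subjects with available PK data and no protocol deviations with relevant impact on PK data". The PD set is built in the same way, so the protocol restricts PK and PD by deviation and leaves safety unrestricted.

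SAP section 4 writes the safety set differently: "All subjects that received study drug and with no protocol deviations with relevant impact on safety will be included in the safety analysis set". Table 4-1 links deviation codes to analysis sets and lists two codes:

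- INC01 is described as "Written informed consent was not obtained prior to performing study assessment", with the consequence "Excluded from safety, PK, PD analysis set". Dosing is not mentioned.
- TRT03 is a subject who was never dosed, also excluded from all three sets.

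Under the table the SAP adds: "If updates to this table are needed, an amendment to the SAP needs to be implemented prior to DBL". On its own role, SAP 1.1 says that it "describes the implementation of the statistical analysis planned in the protocol", and SAP 1.2 says: "Protocol Version v04 is referred for the current SAP". That is the protocol version reviewed here.

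**The concern.** A safety set normally follows exposure: a subject who took the drug is counted whatever else went wrong. The SAP's added clause works against this, because it removes dosed subjects precisely when a deviation bears on safety. Protocol 7.1, for example, mentions deviations that put a patient at significant risk and gives use of an ACE inhibitor as an instance. Read literally, the sentence in SAP 4 would take such a subject out of the safety set.

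INC01 concerns the timing of consent. It covers a subject who had one procedure too early, then consented, was dosed and was followed. The protocol counts that subject and the SAP does not.

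The stated purpose of the study is the clinical safety profile, and the Part 2 primary endpoint is renal safety. Followed as written, the SAP could leave an exposed subject out of adverse event percentages and laboratory, vital sign and ECG summaries in which the protocol would include that subject.

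**Working it through.** The finding rests on comparing the texts. No sample size, power or alpha figure enters it.

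**Side by side, for each type of subject**

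| Subject | Protocol 11.1 | SAP 4 and Table 4-1 | Agree? |
|---|---|---|---|
| Dosed, no deviation | In | In | Yes |
| Dosed, safety-relevant deviation with no listed code | In | Out by the SAP 4 sentence; not listed in Table 4-1 | No |
| Dosed, INC01 | In | Out by Table 4-1 | No |
| Never dosed (TRT03) | Out | Out | Yes |

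Row 2 also shows a mismatch inside the SAP: the sentence sets a general condition, but the table names no code for it. In practice the table governs, so INC01 is the only listed code that can remove a dosed subject. Any further code would need a SAP amendment before database lock.

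**Scale of one removed subject**

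Inputs are the planned sizes. Part 1 has 12 patients at 2:1, so 12 × 2/3 = 8 active and 12 × 1/3 = 4 placebo. Part 2 has about 27 in each active arm and 18 on placebo (protocol 3.1, SAP 1.4). The share of an arm's planned safety denominator lost per subject is 1/n:

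- Part 2 active arm: 1/27 = 3.7%
- Part 2 placebo: 1/18 = 5.6%
- Part 1 active: 1/8 = 12.5%
- Part 1 placebo: 1/4 = 25%

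With no dosed INC01 subjects, the change is 0. These shares assume that the safety summaries use the safety set. They are not renal-event rates.

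**Which outputs are exposed**

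The renal-event proportion has its own denominator, limited to those who completed two weeks or more of treatment (protocol 11.4.3, SAP 7.2.1). The exposure is therefore mainly in the other safety summaries, above all adverse event percentages.

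**The case against.** The strongest reply is that only one consent code is really at issue. Table 4-1 is how SAP 4 is applied, and it contains no code for a safety-relevant deviation. Consent is a condition of entry (protocol 4.2 and 8.1), and protocol 9.1 counts an adverse event only after written consent, so a subject who never consented would add to the denominator with no valid numerator. Monitors verify consent in full (protocol 10.1), so the case should be rare. Significant deviations go into the study report (protocol 13), and adverse event and laboratory data are listed by subject in any case. The visible safety sections of the SAP do not name the analysis set they use, and parts of the SAP are redacted. No affected subject is shown.

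Much of this stands as a limit on impact. The effect is undemonstrated, the arm shares would be the same for any single exclusion, and nothing suggests that the one Part 2 subject with a renal event (SAP 7.2) has INC01.

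It does not remove the conflict. The adverse event definition does not cover the subject who consented late but before dosing; that subject has adverse events and laboratory data that count under the protocol, and INC01 excludes them all the same. Listings do not correct percentages or summary statistics. The safety-set sentence and both table rows are complete as printed, so the contradiction does not depend on redacted text.

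**Conclusion.** The concern holds. SAP 4 and the INC01 row of Table 4-1 are both narrower than protocol 11.1, in a document that says it carries out the protocol's analysis and gives no visible reason for departing from it. TRT03 is consistent with the protocol.

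Confidence in the conflict is high. Its numerical effect is unknown and may be zero, because the documents do not say whether any dosed subject has INC01. The arm shares indicate scale only and rest on planned sizes. This should be corrected, since the rule permits exclusion of exposed subjects in a trial whose purpose is safety, but there is no evidence that any result has been altered.

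**What to change.** In SAP 4, replace the safety-set sentence with the protocol's definition, "The safety analysis set will include all subjects that received any study drug", keep analysis by treatment actually received, and drop the deviation clause for this set. In Table 4-1, let only TRT03 exclude from the safety set. Keep dosed INC01 subjects in it; if consent rules bar pooling their data, report their safety data separately and say so. Deviation-based exclusion can stay for the PK and PD sets.

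The cost is one deleted clause and one edited table row, with no new data. The SAP requires table changes by amendment before database lock, and the documents do not say whether lock has passed. The SAP already reports the Part 2 renal-event count (7.2) and notes that day 28, 24-hour PK samples were not taken (5.2), so it was written with study information in hand and the window may be short or closed. If lock has passed, state the departure from protocol 11.1 in the clinical study report, give the number of dosed subjects with INC01, and present the safety summaries for all dosed subjects, with the same allowance for separate reporting.

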**Table 4-1 Protocol deviation codes and analysis sets**

Category Deviation code	Text description of deviation	Data exclusion
Subjects are excluded from all (safety, PK, PD) analysis in case of these PDs:		
INC01	Written informed consent was not obtained prior to performing study assessment.	Excluded from safety, PK, PD analysis set
TRT03	Subject did not receive any dose of study treatment.	Excluded from Safety, PK and PD analysis set

If updates to this table are needed, an amendment to the SAP needs to be implemented prior to DBL.

## **5 Statistical methods for Pharmacokinetic (PK) parameters**

### **5.1 Variables**

PK parameters Cmax, Tmax, AUClast, AUC0-t, AUCtau and other relevant PK parameters will be considered.

### **5.2 Descriptive analyses**

LHW090/LHV527 plasma concentration data will be listed by Part, treatment, subject, and visit/sampling time point. Descriptive summary statistics will be provided by treatment and visit/sampling time point. Summary statistics will include mean (arithmetic and geometric), SD, CV (arithmetic and geometric), median, minimum and maximum. Concentrations below LLOQ will be treated as zero in summary statistics and for PK parameter calculations. A geometric mean will not be reported if the dataset includes zero values. The day 28, 24 h concentrations will not be included in these analyses since they were not actually collected in this study.

Pharmacokinetic parameters will be listed and summarized by part, treatment and subject. In order to calculate AUCtau, day 28, 24 h concentrations are to be set equal to the day 28, 0 h (predose) concentrations based on the assumption that steady-state had been achieved. Day 28, 24 h PK samples were not actually collected in this study.

Unbound PK concentration and PK parameter data will be listed and summarized for Part 1 as feasible.

### **5.3 Statistical model, assumptions and hypotheses**

No formal statistical analyses will be performed for PK data.

#### **5.3.1 Model checking procedures**

Not applicable.

### **5.4 Graphical presentation of results**

Individual PK profiles and Arithmetic (SD) profile will be provided by part and treatment.

Corporate Confidential Information

## **7 Statistical methods for safety and tolerability data**

### **7.1 Variables**

Corporate Confidential Information

Corporate Confidential Information

The primary safety variable will be the proportion of patients who develop a renal event. The two parts of the study will be analyzed separately. A renal event is defined as a reproducible increase in serum creatinine of  $\geq 0.3$  mg/dL from baseline confirmed on a repeat measurement within 24 to 48 hours.

Change from baseline for serum creatinine will be evaluated and categorized as  $< 0.3$  mg/dL and  $\geq 0.3$  mg/dL. The analysis will be based on central laboratory results. Baseline will be defined as the average of all available pre-dose measurements (excluding screening values).

## 7.2 Statistical model, assumptions and hypotheses

For Part 2, no inferential analysis of renal events will be conducted due to only having 1 subject that fulfilled the criteria. A frequency table will be produced instead.

Historical data from internal Novartis studies in a similar patient population may be used to supplement the information from patients on placebo in the current study.

For each part, change from baseline for serum creatinine data will be analyzed using a linear mixed effects model for repeated measurements. The model will include treatment as a fixed effect, visit as a repeated effect, treatment by visit interaction and baseline as a continuous covariate. An unstructured covariance model will be used. Point estimates and the associated 95% confidence intervals for the difference between treatment and placebo at each visit will be provided.

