Part 2 will be double-blind and placebo-controlled to assess the safety and tolerability of 2 dose levels of LHW090, LHW090 once daily for 4 weeks. Approximately 72 patients will be enrolled in Part 2 and randomized in a 3:3:2 ratio to LHW090 and placebo. Therefore, in Part 2, approximately 27 patients are expected to be randomized to each of the active doses, and 18 patients are expected to be randomized to placebo. Randomization will be stratified by ARB dose (see Appendix 2) at the time of enrollment. Patients who meet the eligibility criteria at screening will have baseline assessments of renal function (serum creatinine, urinalysis) collected on Day -1 prior to beginning the treatment phase on Day 1. Centrally-analyzed laboratory assessments performed at screening will be used to determine patient eligibility for the trial.

The first 16 patients in Part 2 will be domiciled for the first 7 days of dosing to ensure careful monitoring of renal function and pharmacokinetic parameters (see Table 8-3) On Day 7 at the investigator's discretion, the patients will be released to complete the remaining 3 weeks of the treatment phase.

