Study treatment must be discontinued and the patient withdrawn from the study if the patient withdraws consent. Patients may voluntarily withdraw from the study for any reason at any time. They may be considered withdrawn if they state an intention to withdraw, fail to return for visits, or become lost to follow-up for any other reason. If a patient withdrawal occurs for any reason, the Investigator must make every effort to determine the primary reason for a patient's withdrawal from the study and record this information on the CRF.

The Investigator should discontinue study treatment for a given patient or withdraw the patient from study if on balance they believe that continuation would be detrimental to the patient's well-being. Under the following circumstances, individual study treatment must be discontinued and the patient monitored until resolution of the reason for discontinuation according to the Investigator's discretion:

- A reproducible and persistent (confirmed on repeat assessment within 24 48 hr) increase
 in serum creatinine ≥0.3 mg/dL from baseline. Any increases in serum creatinine
 ≥0.3 mg/dL based on local laboratory assessments should trigger repeat assessments of
 serum creatinine until event resolution (e.g. serum creatinine within 10% of baseline) or
 event stabilization. Baseline is defined as the average of all available pre-dose
 measurements.
- Systolic blood pressure <90 mm Hg (must be confirmed on repeat measurement after 30 minutes) or symptomatic hypotension
- Any protocol deviation (e.g. use of an ACE inhibitor) that results in a significant risk to the patient's safety

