11.4.2 Statistical model, hypothesis, and method of analysis

Part 1:

The purpose of the dose escalation in Part 1 is to assess the renal safety and tolerability of multiple doses of LHW090 in patients with moderately impaired renal function starting with the highest single dose tested in renal patients in the first-in-human study before the start of Part 2. Descriptive summary statistics will be provided by treatment group and visit/sampling time point, for change from baseline serum creatinine including the frequency (n, %) of renal events <0.3 mg/dL and ≥ 0.3 mg/dL.

Concentration response modeling may be carried out in Part 1 to assess the correlation of change in serum creatinine with concentration. In the absence of a significant concentration effect on serum creatinine, Part 2 will be initiated Corporate Confidential Information If there is evidence of significant concentration effect, Part 2 of the study may not be initiated or a lower dose may be investigated.

Part 2:

For Part 2, a Chi-square test will be performed to compare the proportion of patients who develop a renal event in the LHW090 pooled active doses, LHW090 individual doses and placebo groups. This analysis will be stratified by ARB dose (see Appendix 2). A logistic model with the baseline ARB dose and the baseline creatinine level as covariates may also be used. P-value and 95% CI of the difference in proportions will be presented. Descriptive summary statistics will be provided by treatment and visit/sampling time point, for change from baseline serum creatinine including the frequency (n, %) of renal events <0.3 mg/dL and ≥ 0.3 mg/dL will be provided.

Historical data from internal Novartis studies in a similar patient population may be used to supplement the information from patients on placebo in the current study.

Analyses stratified by degree of proteinuria (microalbuminuria or macroalbuminuria) and/or history of diabetes may also be conducted.

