11.4.3 Handling of missing values/censoring/discontinuations

For the analysis of the proportion of patients with a renal events described in Section 11.4.3, patients who complete at least 2 weeks of treatment will be included in the denominator. For the analysis of change from baseline in serum creatinine described in Section 11.4.4, all available data will be included and missing data will not be imputed (it will be estimated from the likelihood of the repeated measures model). Patients discontinued by the investigator due to a doubling of serum creatinine from baseline (based on local measurements) will be counted as having a renal event in the primary analysis regardless of the availability of a central serum creatinine value. In case more than 10% of patients drop out before 2 weeks, a sensitivity analysis using multiple imputation techniques may be considered.

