### 7.2.1 Model checking procedures

For the frequency table of the proportion of patients with a renal events, patients who complete at least 2 weeks of treatment will be included in the denominator.

Corporate Confidential Information

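### SAP 7.2 drops the protocol's 95% CI for the Part 2 renal-event difference because only one event occurred, although exact and score intervals can still be computed

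*SAP*

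**What the plan says.** Renal safety is the primary objective of Part 2, and the proportion of patients with a renal event is its endpoint (protocol 2.1, SAP 1.3). Protocol 11.4.2 plans a chi-square comparison of the pooled doses and of each dose with placebo, stratified by ARB dose, and commits to the output: "P-value and 95% CI of the difference in proportions will be presented". A logistic model is optional.

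SAP 7.2 states that for Part 2 "no inferential analysis of renal events will be conducted due to only having 1 subject that fulfilled the criteria", and replaces the analysis with a frequency table. It keeps the repeated-measures model for creatinine change: "Point estimates and the associated 95% confidence intervals for the difference between treatment and placebo at each visit will be provided". Those intervals concern mean creatinine, which protocol 11.4.4 lists as a supportive analysis. They do not concern the event proportion.

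For the frequency table, SAP 7.2.1 says that "patients who complete at least 2 weeks of treatment will be included in the denominator", the same limit as in protocol 11.4.3. Under protocol 7.1, after a confirmed creatinine rise, "individual study treatment must be discontinued and the patient monitored until resolution of the reason for discontinuation". The only visible rule for counting a patient who stopped early is in protocol 11.4.3: patients taken off treatment because creatinine doubled "will be counted as having a renal event in the primary analysis regardless of the availability of a central serum creatinine value".

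**The concern.** The p-value and the interval are separate commitments, and the SAP's reason touches only the first. A chi-square approximation fails with one event, and the optional logistic model cannot estimate a treatment effect when one group has no events. An interval for a difference in proportions needs neither.

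The study is meant to decide whether the safety profile supports further development. A bare count of one reads as reassurance without showing how far the reassurance goes, and with 18 placebo patients and 27 per dose it does not go very far.

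The denominator is a related point, which comes from the protocol and not from the SAP change. A confirmed event stops treatment, and only patients with at least 2 weeks of treatment are counted. Read literally, a patient whose event came early leaves the table because of the event.

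**Working it through.** **Inputs.** Planned sizes are 27 per dose and 18 on placebo, so 54 pooled active (protocol 3.1 and 11.6). Part 2 had one event in total (SAP 7.2). The event's arm, the number completing 2 weeks and the ARB stratum sizes are not given. Both arms are therefore run at planned size, with an assumed 20% loss as sensitivity.

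**The plan's own figure.** Protocol 11.6 states 82% power for 3% against 28%, 54 against 18, one-sided 10%.
- Pooled rate: (54×0.28 + 18×0.03)/72 = 0.2175.
- Null SE: √[0.2175×0.7825×(1/54 + 1/18)] = 0.1123.
- Alternative SE: √[0.28×0.72/54 + 0.03×0.97/18] = 0.0731.
- Continuity correction: 0.5×(1/54 + 1/18) = 0.0370.
- Power: Φ[(0.25 − 0.0370 − 1.2816×0.1123)/0.0731] = Φ(0.944) = 82.7%.

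The stated power is reproduced, with the continuity correction, from the sizes used below.

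**Why the chi-square fails.** Expected events with one in total: 54/72 = 0.75 on active and 18/72 = 0.25 on placebo.

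**Score interval (Miettinen-Nurminen).** Solve for δ in (p̂₁ − p̂₂ − δ) / √{[p̃₁(1−p̃₁)/n₁ + p̃₂(1−p̃₂)/n₂]·N/(N−1)} = ±1.96, where p̃ are the maximum-likelihood rates constrained to differ by δ.

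**Exact unconditional interval.** Order all tables by the score statistic at each δ, and maximise each tail probability over the unknown placebo rate. Keep δ if both tails exceed 2.5%. The limits were found in steps of 0.2 points. A recheck in 0.05-point steps moved no planned-size limit by more than 0.15 points.

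Active minus placebo, percentage points, unstratified:

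| Scenario | Difference | Score 95% CI | Exact 95% CI |
|---|---|---|---|
| 1/54 vs 0/18 (event on active) | +1.9 | -16.0 to +9.9 | -18.6 to +10.4 |
| 0/54 vs 1/18 (event on placebo) | -5.6 | -25.9 to +1.5 | -27.2 to +3.4 |
| 1/27 vs 0/18 (dose with the event) | +3.7 | -14.5 to +18.5 | -15.0 to +19.0 |
| 0/27 vs 0/18 (the other dose) | 0.0 | -17.9 to +12.7 | -18.4 to +13.0 |

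With an assumed 20% loss and the event on active (1/43 vs 0/14), the score interval is -19.7 to +12.2 and the exact upper limit is about +12.8.

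**Single groups, Clopper-Pearson 95% upper limits.** 1/54: 9.9%; 0/54: 6.6%; 1/27: 19.0%; 0/27: 12.8%; 1/18: 27.3%; 0/18: 18.5%. For zero events the formula is 1 − 0.025^(1/n); for n = 18 it gives 1 − 0.025^(1/18) = 18.5%.

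**Method and stratification.** Between score and exact, the pooled limits differ by up to 18.6 − 16.0 = 2.6 points. A stratified score interval (Mantel-Haenszel weights, two strata, assumed splits from 11% to 89%) differs from the unstratified one by at most 0.8 points. With one event, the choice of method matters more than stratification.

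**Denominator.** If the event was on active and that patient stopped before 2 weeks, a literal reading of SAP 7.2.1 turns 1/54 into 0/53.

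**The case against.** The sponsor can fairly say that the change is disclosed with its reason, that creatinine intervals by visit remain, and that optional historical placebo data are kept. A reader could also compute unstratified limits if counts are shown by arm. All of this stands, and it limits the weight of the point. It does not supply the promised interval: the creatinine model answers a different question, and historical data are not an interval.

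Parts of the SAP near this text are redacted. Further table details may sit there, but the visible sentence puts the frequency table in place of the inferential analysis and so leaves no evident room for a confidence interval.

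A score interval is itself a large-sample method at expected counts of 0.75 and 0.25. That stands, and it is why the fix uses the exact interval.

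Three stronger readings are tempting, and the documents do not support them:
- **A 25-point excess has been ruled out.** Every pooled upper limit above lies below 25 points. But 25 points is the difference the trial was sized to detect. The protocol sets no rule-out margin, and the limits use planned or assumed sizes.
- **The interval was dropped to hide an unfavourable result.** The choice followed knowledge of the event count, but the SAP gives the reason openly and does not say which arm had the event.
- **The one event was lost through the 2-week rule.** Its timing is not stated.

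**Conclusion.** The point holds as a precision and reporting gap on the Part 2 primary endpoint, and it should be corrected. One event justifies dropping the chi-square p-value. It does not justify dropping the 95% interval.

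At planned sizes, the missing interval would show a pooled excess on active of up to about 10 points as still compatible with the data if the event was on active. For a single dose with the event, that figure is about 19 points. These limits rest on full planned denominators, an assumed arm for the event and no stratification. They describe precision only, and no conclusion of the trial changes.

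The denominator rule adds a smaller uncertainty whose effect on the one event cannot be determined from the documents.

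**What to change.** Replace the SAP 7.2 sentence with:

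> No chi-square p-value will be given. The frequency table will show, for each dose, pooled active and placebo, the number and proportion of patients with a renal event with a Clopper-Pearson 95% CI, and for each active-minus-placebo difference an exact unconditional 95% CI (inversion of the score statistic), unstratified as a stated departure from the ARB-dose stratification because there is one event.

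In SAP 7.2.1, keep the 2-week denominator and add a second version of the table with all treated Part 2 patients as denominator. This is better than adding back only early stoppers who had an event. That would make inclusion depend on the outcome and bias the proportion upward, by a rule set after the event was known. The all-treated version counts early stoppers without an event as event-free, so the two versions should be read together.

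The cost is a few lines of SAP text, seven intervals (four groups, three differences) and one extra table version. No new data are needed.
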